# 3.3 Randomization

Subjects who have been enrolled in the study will be randomized within 2 days after successful placement of a new arteriovenous graft. Administration of the study drug should begin immediately following randomization. The optimal time for randomization and initiation of study medication would be in the postoperative recovery room after verification that a graft was placed. If the surgeon reports that the graft thrombosed in the operating room or in the recovery room, the patient should not be randomized. Subjects will be randomized to either Aggrenox or matched placebo in a ratio of 1:1. Randomization will be stratified by Clinical Center and by access (lower arm or at another site). A random permuted block design will be used to assure approximate balance over time. Randomization will be performed via the internet using a Web browser following verification of eligibility by the Data Coordinating Center. Stratification based on Clinical Center is designed to minimize the influence that differences in baseline risk between different centers might have on study outcome. While one source of variability is likely to be surgical expertise (62), the number of access procedures done by each surgeon is expected to be so small that stratification by surgeon is not likely to be feasible. The location of the graft in the upper or lower arm has been shown to strongly influence graft survival in some studies and thus randomization will also be stratified by this variable (55, 63, 64). Since leg grafts and other heroic graft sites (e.g., necklace graft) have a high flow rate, they will be categorized as an upper arm graft for the purpose of stratification (63).

Use of angiotensin converting enzyme inhibitors has recently been reported in two retrospective studies to have a strong effect to prevent access failure (119, 120). The results are preliminary, however, the use of ACE inhibitors in dialysis patients is increasing. If ACE inhibitors or ARBs do have a large effect on access survival then this could impact on the response to Aggrenox. Therefore, whether a patient was on an ACE inhibitor or ARB at baseline will be included as a prespecified covariate in the primary analysis. The use of these agents will not be controlled and may change during the course of the study. The ongoing use of these agents will be recorded at the monthly visits and that data will be used to further analyze for a possible relationship between use of these agents and access failure. In addition, hypoalbuminemia has been reported to be a strong risk predictor of access failure (55, 63, 64). Therefore, serum albumin at baseline will be included as a second prespecified covariate in the primary analysis. Other potential prognostic factors such as diabetes and vascular disease have not been consistently shown to be strong predictors of access failure, and will not used as stratification factors or as covariates in the primary analysis.

# 3.4 Blinding

Treatment assignment will be masked to both patients and study personnel. Aggrenox and matching placebo will be provided by Boehringer-Ingelheim. Dipyridamole produces vasodilation that might lead to an increase in access blood flow detectable by flow monitoring. However, the difference in access flow rate between subjects will likely be larger than the effect of dipyridamole. Since the study involves new grafts, there will be no prior baseline access flow measurement for comparison and therefore it is unlikely that the blinding will be unmasked by flow monitoring. Initiation of dipyridamole will cause transient headache in some patients that could unmask the blinding in those patients. The aspirin component of Aggrenox might also unmask the study blind due to increased

difficulty with hemostasis at the end of dialysis. However, patients who receive Aggrenox or placebo at the time of receiving a new access will not have a baseline comparison to discern whether the study drug has altered hemostasis. Moreover, aspirin is commonly used in ESRD patients and this will tend to obscure any noticeable difference between the study patients on Aggrenox and the general hemodialysis population.

Aggrenox has a small dose of aspirin that could predispose to bleeding. We anticipate that unblinding may be required in the following two circumstances: 1) prior to the performance of emergency surgery, and 2) if there is life-threatening hemorrhage where the transfusion of platelets to reverse the antiplatelet effects of therapy is indicated. When it is absolutely necessary that a study medication code be released, the Data Coordinating Center will reveal the medication for a given patient to the study nephrologist at the facility. After unblinding, the patient should be continued in the trial on study medication if the subject did not have a major or life-threatening bleed and there are no other medical contraindications to doing so.

#### 4. STUDY TREATMENT PLAN

#### 4.1 Study Visits

Subjects should be seen prior to creation of the access for enrollment and collection of baseline data. The subject will be evaluated again within 2 days after creation of the new access to confirm that an eligible graft had been placed and is patent. If the access is patent, the subject will be randomized into the study and the first months supply of study medication will be provided. The patient will be asked to take their first dose of medication at that time.

Following randomization, subjects will be seen at monthly intervals throughout the duration of the study. It is anticipated that most subjects will be undergoing hemodialysis and will be seen at the time of a scheduled hemodialysis session. For subjects on hemodialysis, each monthly visit will include a measurement of access flow rate along with collection of study data including an assessment of access related procedures, complications, hospitalizations and compliance with the study medication (Section 6.2 below). For those subjects not yet on hemodialysis a monthly visit will need to be arranged to assess access patency and collect study data.

The subject will remain on study medication until the primary endpoint is reached, at which point the medication will be terminated. The monthly visit schedule will continue until the first regularly scheduled monthly visit following the primary endpoint. At closeout, the functional status of all accesses and survival of all patients that had been enrolled in the study will be determined and if total site failure or death has occurred, the time of these events will be recorded. Each monthly visit will include an assessment of potential adverse events.

#### 4.2 Study Drug Administration

The first dose of study medication should be administered starting within 2 days of access creation. The Aggrenox or matched placebo should be taken as one pill twice a day. Assuming there are no reasons for early termination of the study medication, the study medication should be administered throughout the duration of the study until the primary endpoint occurs or study termination.

Each unit will need to establish a mechanism for storing the study medication and for dispensing the study drug to the subject within 2 days after surgery and then monthly thereafter. The study coordinator or the investigational pharmacy may handle storage and dispensing of the study medication as appropriate for each unit. The study medication will be mailed from a central pharmacy to the designated study coordinator or investigational pharmacy at each unit.

#### 4.3 Intercurrent Events and Interruptions in Treatment

At the time of enrollment, patients will be provided with an information card containing a description of the study and study personnel contact information. The information card should facilitate rapid communication with study personnel if adverse events occur or treatment interruptions need to be considered.

#### 4.3.1 Bleeding

Aggrenox has a small dose of aspirin that will increase the risk of bleeding. Bleeding will be classified as either minor, intermediate, major, life-threatening or fatal. Minor bleeding events are episodes of bleeding that did not require an event-related visit or follow-up or discontinuation of the study drug. Intermediate bleeding is a bleeding event that does not meet criteria for a major bleed but required an event-related visit with a health care provider or temporary discontinuation of study medication. Examples of minor or intermediate bleeds might include superficial cuts, abrasions, bruises, nose bleeds, or vaginal bleeding events. The presence of a hemoccult positive stool alone that leads to non-emergent evaluation such as a colonoscopy and is not associated with a 2 g/dl drop in hemoglobin or the need for a transfusion will be considered an intermediate bleeding event. Major bleeding is defined as a confirmed retroperitoneal, intra-articular, intraocular, or intracranial bleed or any bleed that leads to a drop in hemoglobin by 2 g/dl and requires hospitalization or the need for a transfusion, causes a symptomatic intracranial hemorrhage, or requires a transfusion of more than 4 units of packed RBCs or whole blood. Fatal bleeding is any bleed that causes or precipitates death.

Management of bleeding should be handled as for a patient on aspirin. For minor episodes of bleeding (e.g., superficial abrasion or nose bleed) conservative measures to control the bleeding should suffice without the requirement for discontinuing study medication. Short-term discontinuation of study medication during an intermediate bleeding episode with re-institution when stable is allowed. If the patient has a major or life-threatening bleed the study medication will be discontinued and not restarted. In the event of a cerebrovascular accident occurring during active treatment, computed tomography or magnetic resonance imaging should be performed to exclude intracerebral hemorrhage. For intermediate bleeds the decision to stop study drug will be made by the physician(s) caring for the patient. If the patient has a major or life-threatening bleed the study medication will be discontinued and not restarted unless the bleed is caused by either a surgical procedure or trauma and it is established 1) that the cause of bleeding has been eradicated, and 2) that the bleeding event does not reflect an underlying bleeding tendency or predispose to recurrent bleeding. Study drug resumption in this situation must be approved by the physician(s) caring for the patient. Bleeding events will be actively monitored and recorded by the study coordinator throughout the patient's participation on the study. An expert panel will review all major and life-threatening bleeds as well as a randomly selected subset of other bleeding events.

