#### 4.3.6 Discontinuation of Therapy

Adverse events leading to cessation of study drug, but not termination from the study will include:

- 1. Development of an intestinal ulcer or gastrointestinal bleeding while on the study medication.
- 2. An adverse event attributed to the study medication such as intolerable persistent headache, diarrhea or dizziness without other etiology that does not respond to medical management.
- 3. A bleeding disorder (e.g., a major or life-threatening bleed) that contraindicates the continued use of Aggrenox.
- 4. A new medical requirement for long-term anticoagulation or antiplatelet therapy other than aspirin.
- 5. A new medical requirement for using Aggrenox or dipyridamole.

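### The study-drug rules after bleeding conflict in two defined situations: surgical or traumatic major bleeds, and gastrointestinal bleeds below major

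*Protocol*

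**What the plan says.** Study drug after a bleed is governed in three places in the Protocol.

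**Section 4.3.1 (Bleeding)** names five grades: minor, intermediate, major, life-threatening and fatal. A positive stool hemoccult test on its own, with neither a 2 g/dl hemoglobin fall nor a transfusion, is graded intermediate. The management paragraph then says:

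- for intermediate bleeds, "Short-term discontinuation of study medication during an intermediate bleeding episode with re-institution when stable is allowed", and "For intermediate bleeds the decision to stop study drug will be made by the physician(s) caring for the patient";
- for the higher grades, first: "If the patient has a major or life-threatening bleed the study medication will be discontinued and not restarted";
- three sentences later, for the same grades, that study drug "will be discontinued and not restarted unless the bleed is caused by either a surgical procedure or trauma", with two further conditions (the source has been dealt with; the bleed signals neither an underlying tendency nor a risk of recurrence) and the requirement that "Study drug resumption in this situation must be approved by the physician(s) caring for the patient".

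**Section 4.3.6 (Discontinuation of Therapy)** lists adverse events that lead to cessation of study drug while the patient stays in the study. Item 1 is "Development of an intestinal ulcer or gastrointestinal bleeding while on the study medication", with no grade and no route back to treatment. Item 3 gives a major or life-threatening bleed as its example of a bleeding disorder that contraindicates further use, and does not mention the exception for surgery or trauma.

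**Section 3.4 (Blinding)** says that after the code is broken the patient should be "continued in the trial on study medication if the subject did not have a major or life-threatening bleed" and nothing else contraindicates it. It too is silent on the exception.

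**The concern.** A coordinator facing a bleed should find one instruction. Here the answer can depend on which sentence or section is consulted. Bleeding is the main expected harm of the active drug (Section 6.2.6), so these rules will be used in practice.

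Two things are at stake. The first is safety: one patient may be kept on, or returned to, study drug when another part of the same protocol says it stops, and another may lose treatment that the protocol would have allowed. The second is data quality: what happens to exposure after a first bleed feeds into recurrent bleeding, tolerability and adherence. If sites differ in that step, those summaries partly reflect how the protocol was read.

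**Working it through.** The Protocol states no figure on this point and no arithmetic applies to the conflict itself. The check is to take each type of bleed and read off what each section requires.

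| Bleed | Section 4.3.1 | Sections 4.3.6 and 3.4 | Consistent? |
|---|---|---|---|
| Major or life-threatening, not due to surgery or trauma | Both statements: stop, no restart | Item 3: cessation; 3.4: does not provide for continuing | Yes |
| Major or life-threatening, due to surgery or trauma, both conditions met | First statement: stop, no restart. Second statement: restart possible with approval | Item 3 and 3.4 mention such bleeds without the exception | **No** |
| Intermediate, not gastrointestinal | Physician decides; restart allowed | Item 1 does not apply | Yes |
| Intermediate, overt gastrointestinal | Physician decides; restart allowed | Item 1: cessation | **No** |
| Positive stool hemoccult test alone | Graded intermediate, so physician decides | Item 1 applies if the finding counts as gastrointestinal bleeding, which is not stated | Unclear |

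**Situation 1.** The operative words recur almost unchanged: once as a flat bar, once as "not restarted unless the bleed is caused by either a surgical procedure or trauma". The first statement does not point forward to an exception, and the second does not say that it qualifies the first. Section 3.4 matters because it expects the code to be broken before emergency surgery and in life-threatening hemorrhage, which is where surgical and traumatic bleeds are likely to arise.

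**Situation 2.** Item 1 of Section 4.3.6 makes gastrointestinal bleeding, ungraded, a cause of cessation. Section 4.3.1 makes stopping discretionary for anything intermediate, and for minor bleeds expects conservative measures to be enough. A gastrointestinal bleed below major therefore falls under a mandatory stop in one section and a discretionary one, or none, in the other. The clash over stopping is plain. The clash over restarting is softer: Section 4.3.6 gives no route back but does not itself call the cessation permanent.

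**Can the conflict be sized?** That would need the share of bleeds that are major and caused by surgery or trauma, and the share that are gastrointestinal and below major. The Protocol gives neither. The nearest figures are in Section 1.5:

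- In the unpublished German dialysis trial, bleeding of any kind led to discontinuation in 38/451 = 8.4% on active drug and 23/452 = 5.1% on placebo (the Protocol prints 5.0%). This covers all bleeding and is not divided by cause, site or grade.
- In the cited hypertension trial, 72 of 129 non-fatal major bleeds on aspirin were gastrointestinal (72/129 = 56%). These are major bleeds, so they do not measure the sub-major category in dispute.

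The figures show that bleeding is a common reason to stop drug and that the gut is a common site. They do not give the size of the conflict.

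**The case against.** **The later sentence is simply an exception.** Specific text ordinarily qualifies general text, and the second statement in Section 4.3.1 is the fuller one. Many readers would apply it without difficulty. This softens situation 1 to poor drafting, though a reader who stops at the first sentence still acts differently from one who reads on. It does nothing for situation 2, where neither section refers to the other.

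**Sections 3.4 and 4.3.6 item 3 do not contradict the exception.** Largely correct. Section 3.4 concerns continuation after unblinding and says nothing about later resumption. Item 3 is limited to bleeds that contraindicate further use, and a bleed meeting the exception might not. Both omit the exception without denying it. They belong in the reconciliation but are not independent contradictions.

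**Item 1 was not meant to reach trivial findings.** Possibly. Whether a positive hemoccult test alone counts is a matter of interpretation. Overt gastrointestinal bleeding below major is still caught by the words as they stand.

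**There are safeguards.** Treatment is masked, randomization and the primary Cox model are stratified by center, an expert panel reviews all major and life-threatening bleeds (Section 4.3.1), and a committee reviews reasons for permanent withdrawal (Section 4.3.3). These limit the damage to the comparison: divergent readings would be expected to affect both arms, adding noise more than evident bias. Both reviews look at events or decisions that have already occurred, so neither gives a site a single rule to apply at the time.

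**Two stronger readings are tempting and not supported.** A reader might infer that the bleeding rules conflict throughout; the table shows that they do not. A reader might also infer that the ambiguity raises dropout and erodes power. The 15% annual dropout in the sample-size section is an all-cause assumption taken from experience in large trials and is not built from any bleeding rule. Nothing in the Protocol says how far this ambiguity would move it.

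**Conclusion.** The conflict is real and confined to two situations: a major or life-threatening bleed caused by surgery or trauma, and a gastrointestinal bleed below major. The second is the firmer, because reading one passage as an exception to another does not resolve it.

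The consequence is that compliant sites can manage the same bleed differently, which bears on patient safety and on the consistency of exposure and bleeding data. The primary analysis keeps patients in their randomized groups whatever their compliance (Section 9.2.2.2), so its validity is not in question. The number of patients affected cannot be derived from the Protocol, and no loss of power is claimed.

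The conclusion rests on the text alone, with one assumption: that gastrointestinal bleeding in Section 4.3.6 item 1 carries its ordinary meaning and is not silently limited to major bleeds. If it were so limited, situation 2 would largely disappear, but the Protocol would need to say so. The point should be corrected because it concerns the main expected harm and is cheap to put right.

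**What to change.** The sponsor's clinical leads should reconcile Sections 3.4, 4.3.1 (both the grading and the management paragraphs) and 4.3.6 items 1 and 3 into one statement organized by bleed grade and site. For each combination it should say whether stopping is mandatory or discretionary, whether resumption is possible, and who approves it. It should cover gastrointestinal bleeds below major explicitly, say whether a positive hemoccult test alone counts as one, and say whether the surgery-or-trauma provision also applies after unblinding. Wording that conflicts with the agreed statement should be removed, and the other sections should refer to it.

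Which rule to adopt is for the clinical leads; no preference is expressed here.

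Cost: a short protocol amendment, with the IRB approval that Section 11.1 requires before implementation, and a notice to sites. The sample size and the primary analysis need no change.

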# 6.2.3 Monthly Adverse Event Monitoring

Adverse events will be recorded at the monthly visits. Subjects will be asked the following questions:

- 1. Have you had any problems with your study medication? Describe them.
- 2. Have you had any hospitalizations? When and what was the reason?
- 3. Have you had any other new significant health problems? Describe them.
- 4. Have you had any episodes of significant bleeding?
- 5. Are you having any gastrointestinal symptoms such as heartburn or abdominal pain?

The responses to all these questions will be recorded and an assessment will be made as to whether the event is related to the study medication. For any hospitalizations or emergency room visits the medical record will be reviewed to determine the cause of the visit and whether it was likely related to the study medication. Particular attention will be given to whether a bleeding event precipitated the visit or hospitalization. For patients that might be questionable historians, the dialysis nurse caring for the patient will be asked whether they are aware of any adverse events, hospitalizations, or transfusions that have occurred in the preceding month. In addition, the patient dialysis logs will be examined to determine if the patient missed any sessions and the patient will be asked the reason for the absence. Serious adverse events are those that result in any of the following outcomes: death, a life-threatening adverse experience, inpatient hospitalization or prolongation of existing hospitalization, a persistent or significant disability/incapacity, or a congenital anomaly or birth defect. All serious adverse events will be reported to the DCC within 24 hours of study personnel learning of the event.

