#### 6.2.6 Quality Control of Clinical Center Data

Each clinical study site will be visited once during year one and every other year for the remainder of the study. The site visit will consider recruitment, retention, patient compliance, adverse event monitoring and clinical center adherence to study procedures. During the data audit portion of the site visit, site visitors will examine a random subset of site clinical data for which source documentation would normally be available, such as date of birth and local laboratory data. Data on source documents at the clinical center will be compared with data in the DAC Study Database.

Bleeding is the major expected risk of therapy with Aggrenox. For purposes of safety and adverse event analyses, categorization of bleeding events will be made based on information transmitted from the clinical centers on the data forms with additional information obtained from source documents as needed. To assure that bleeding events that result in death are properly documented there will be central review of data on any subject who has had a bleeding event recorded in the study database within 30 days prior to death. The study's Data Coordinating Center will notify investigators about any subject who meets these criteria. The center will then send primary data including any emergency room or hospital discharge summaries relevant to the bleed as well as documentation relating to the subsequent death. This information will be reviewed by two independent physician study investigators to determine whether the cause of death was related to the prior bleed.

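### Full panel review of bleeds depends on the category already assigned, so a major bleed categorized too low is checked only by chance, and the panel's verdict is not tied to the analysed category

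*Protocol*

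**What the plan says.** Section 4.3.1 sorts bleeds into minor, intermediate, major, life-threatening and fatal. Intermediate is defined partly by exclusion, as a bleed short of the major criteria. Those criteria are mostly objective: certain anatomical sites, or for example "any bleed that leads to a drop in hemoglobin by 2 g/dl and requires hospitalization or the need for a transfusion". The section then sets two levels of review, full for the top categories and sampled for the others: "An expert panel will review all major and life-threatening bleeds as well as a randomly selected subset of other bleeding events". It does not say who assigns the category that decides this, how large the sample is, or whether the panel may change a category.

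Section 6.2.6 opens its paragraph on bleeding with "Bleeding is the major expected risk of therapy with Aggrenox". For the safety analyses, it says, "categorization of bleeding events will be made based on information transmitted from the clinical centers on the data forms"; the same sentence adds source documents where needed. The panel is not mentioned there. The section adds a separate check for fatal cases: "there will be central review of data on any subject who has had a bleeding event recorded in the study database within 30 days" before death, with two physicians judging whether the bleed caused the death.

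Section 6.2.3 adds a check at the site: "For any hospitalizations or emergency room visits the medical record will be reviewed to determine the cause of the visit". Section 3.4 masks study personnel to treatment.

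**The concern.** Review is meant to catch bleeds in the wrong category. Here the category itself decides whether a bleed is certain to be reviewed. A bleed wrongly called major will be seen. A bleed that meets the major criteria but was recorded as intermediate will be seen only if it is drawn. Misplacement at that border is plausible, because the major definition in 4.3.1 strings several and/or conditions together, and intermediate is whatever falls short of it.

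The two sections also leave the use of the panel's verdict open. If the panel's category is analysed, verification is unequal. If the category in 6.2.6 is analysed without the panel, the panel's reading does not reach the analysis. Either way, a recorded bleed that qualifies as major can be left out of the major count. The point is about recorded bleeds placed too low, not about bleeds that were never recorded.

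Few major bleeds are expected, so a modest loss matters for the comparison of harm. The absolute excess would be reported too small, and real harm would be harder to show.

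**Working it through.** The protocol gives no power figure for bleeding, so there is none to reproduce. Two checks follow.

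**1. Does the rule fix the direction of correction?**

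Let R be the number of other bleeds per bleed categorized major, o the share of major-categorized bleeds that are over-graded, u the share of the others that are under-graded, and f the sampled fraction. Suppose the panel may regrade. Per 100 major-categorized bleeds:

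- downward corrections = 100·o
- upward corrections = 100·f·R·u
- still placed too low = 100·(1−f)·R·u
- break-even fraction f* = o/(R·u)

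R can be approximated from the stroke-prevention trial tabulated in Section 1.5: (144−27)/27 = 4.33 on dipyridamole plus aspirin, and (74−7)/7 = 9.57 on placebo. The protocol gives no o, u or f. I assume o = 10% and u = 5%:

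| R | f | Down | Up | Still too low | True major | Missed |
|---|---|---|---|---|---|---|
| 4.33 | 0.10 | 10 | 2.2 | 19.5 | 111.7 | 17% |
| 4.33 | 0.50 | 10 | 10.8 | 10.8 | 111.7 | 10% |
| 9.57 | 0.10 | 10 | 4.8 | 43.1 | 137.9 | 31% |
| 9.57 | 0.50 | 10 | 23.9 | 23.9 | 137.9 | 17% |

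Here f* is 0.10/(4.33 × 0.05) = 0.46, or 0.10/(9.57 × 0.05) = 0.21. Over o = 5–20% and u = 2–10%, it runs from 0.05 to above 1. So the direction is not determined. What holds for every f below 1 and u above 0 is that some bleeds stay too low.

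**2. What could it cost in power?**

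*Person-years.* Section 9.1 gives 1056 subjects (528 per arm), 3 years' accrual within 4 years, one-year failure 0.54 on placebo, a 25% reduction, 22% loss, 15% dropout and 1% dropin. The placebo hazard is −ln 0.46 = 0.7765 per year and the loss hazard −ln 0.78 = 0.2485, so λ = 1.025. Mean follow-up is (1/λ)[1 − (e^(−λ) − e^(−4λ))/(3λ)] = 0.867 year, and 528 × 0.867 = 458 person-years. On Aggrenox, with hazard 0.75 × 0.7765 = 0.582 and dropouts moved to the placebo hazard, numerical integration gives 526. Follow-up is counted to the first access event, because Section 4.5 ends participation at the next monthly visit. The addendum's longer recruitment is not used; with the same 1056 subjects, the same formula gives about 441 on placebo.

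*Expected bleeds.* Section 1.5 gives 1–1.5% per year serious hemorrhage on placebo and a 2–4-fold increase. At 1.25% and threefold: 0.0125 × 458 = 5.7 against 0.0375 × 526 = 19.7.

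*Capture.* If a share s of true major bleeds is categorized correctly, the share counted is s + f(1−s). Both s and f are assumptions:

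- s = 0.95, f = 0.5: 0.975
- s = 0.9, f = 0.1: 0.91
- s = 0.8, f = 0.1: 0.82
- s = 0.7, f = 0.1: 0.73

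*Power.* I used an exact conditional binomial test of the two Poisson counts (null share 526/984), two-sided 5%, doubling the smaller tail, with both means multiplied by the capture:

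| Placebo rate, increase | All counted | 0.975 | 0.91 | 0.82 | 0.73 |
|---|---|---|---|---|---|
| 1.25%, 3-fold | 0.64 | 0.625 | 0.59 | 0.53 | 0.48 |
| 1.25%, 2-fold | 0.22 | 0.21 | 0.20 | 0.17 | 0.15 |
| 1.25%, 4-fold | 0.91 | 0.90 | 0.88 | 0.83 | 0.78 |

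In the central case the loss is about 1 to 16 points. The expected excess falls from 19.7 − 5.7 = 14.0 bleeds to 0.73 × 14.0 = 10.2 at the lowest capture. The ratio of the two rates does not change, since both are multiplied by the same factor.

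**The case against.** A reader might infer that corrections will run mostly downward. The protocol does not support that. It gives no subset size and no error rates, and it does not say that the panel regrades. The first check shows that either direction is possible.

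A reader might also infer that under-graded major bleeds simply stay uncounted. That is too strong. The random subset finds some of them and could be used to estimate how many there are. Section 6.2.6 speaks of transmitted information and source documents, which can be read as categorization from reported facts rather than acceptance of a site's label. Hospital and emergency records are reviewed under 6.2.3, bleeds shortly before death are reviewed whatever their grade, and hospitalizations are serious adverse events sent to the coordinating center within 24 hours. The objective criteria also make gross under-grading less likely. These safeguards narrow the gap but do not close it. The review before death asks about the cause of death, the record review asks about the cause of the visit and its relation to the drug, and neither is described as regrading a nonfatal bleed.

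Nor does the protocol name major bleeding its main safety outcome; it calls bleeding the major expected risk.

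It can fairly be said that s and f are invented, that the 2–4-fold range moves full-count power from 0.22 to 0.91, far more than capture does, and that the trial behind this range defined severe bleeding by transfusion, unlike this protocol. All of that stands and limits the size of the point.

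Finally, the subset fraction and regrading rules may sit in an analysis plan or panel charter, so their absence is not held against the protocol. The selection rule and the source of the analysed category, however, are both fixed in the protocol itself.

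**Conclusion.** The point holds in a limited form. Section 4.3.1 makes certain review conditional on the category under review, so a recorded bleed that meets the major criteria but was categorized lower is checked only by chance. Section 6.2.6 does not connect the panel to the category analysed.

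Because grading is masked, under-grading should be similar in the two arms and the risk ratio roughly kept. The count of major bleeds, the absolute excess and the power to show harm can be reduced. Under assumed capture of 73% to 97.5%, the loss is about 1 to 16 points from 64%, at 1.25% per year on placebo and a threefold increase. At the favourable end it is negligible, and nothing in the protocol says where in the range the trial would fall. This is a worthwhile, low-cost improvement rather than a defect that invalidates the safety comparison.

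**What to change.** In Section 4.3.1, keep full panel review of every bleed categorized major or life-threatening. Add every other recorded bleed, whatever its category, that has any of these features:

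- a hospitalization or emergency visit for the bleed;
- a transfusion;
- a hemoglobin fall of at least 2 g/dl attributed to the bleed;
- a location in the retroperitoneum, a joint, the eye or the skull.

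Keep the random subset for the remainder. In Section 6.2.6, state that the panel's category is the one used in the safety analyses.

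The cost is some added time for the existing panel, since some bleeds with these features will prove not to be major. Hospital and emergency records and monthly hemoglobin are already collected under Sections 6.2.2 and 6.2.3. The change concerns only review and analysis, and leaves the handling of study drug after a bleed as it is.
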